4.3.4 Randomization

Not applicable.

4.3.5 Subject Disposition

Participant disposition will be summarized by study group and overall using Screened, Enrolled, mITT, and Safety populations. The number and percentage of participants will be presented for mITT and Safety populations. The denominator for percentages will be the number of participants enrolled.

Discontinued participants will be summarized by discontinued reasons.

A listing for disposition will include the participants who are enrolled and will cover the following information: informed consent date population assigned (mITT and/or Safety), study completion status and reason for discontinuation.

4.3.6 Demographics and Baseline Characteristics

Age (years) will be summarized as both a continuous and categorical (<=40 years, >40 years) variable. Gender, race, and ethnicity will be summarized for safety and mITT populations and listed for the safety population.

The following baseline characteristics will be derived and summarized for safety and mITT populations:

- DH diagnosis (from OHQ):
 - self-reported DH without previous diagnosis by a dentist
 - \circ self-reported DH with previous diagnosis by a dentist
- Use of anti-sensitivity toothpaste (from OHQ):
 - Non-users will include subjects who are not currently using a sensitivity toothpaste e.g., first-time user
 - Intermittent users will include subjects who sometimes use a sensitivity toothpaste
 - current users will include subjects who regularly (daily) use a sensitivity toothpaste
- Frequency of DH symptoms (from SQ):
 - Frequent = Several times a day, Once a day, Several times a week

	HLN-003 Statistical Analysis Plan
Page 13 of 17	Version 1.0

 Less Frequent=Once a week, Several times a month, once a month, less than once a month

All categorical responses to the Screening Questionnaire and Oral hygiene Questionnaire will be summarized for the safety and mITT populations and listed for the safety population.

4.3.7 Compliance

Study product compliance and compliance to the study schedule will be tabulated and summarized for the safety population.

Summaries will include a simple yes/no frequency (and percent) count at each timepoint:

- Summary of completion to each study schedule and assessments (yes/no)
- Summary of product usage according to product instructions (more than 5 days/5 days or fewer)
- Summary of number of tubes remaining at the end of the study (number remaining) into three categories: 2 or less tubes, 3 to 6 tubes, and more than 6 tubes.

A listing of number of tubes remaining per subject will also be produced for the safety population.

4.3.8 Prior and Concomitant Medications

All concomitant medications will be coded using WHO Drug dictionary.

Prior and concomitant medications taken during the study will be listed for the safety population. The listing will include reason for the medication as well as the start and stop date/time will be presented WHO Drug Class and Preferred term.

4.3.9 Medical History

All medical history will be coded using MedDRA dictionary.

Medical history will be listed for the safety population. The listing will include start and end date, ongoing status, and treatment status, and will be presented with System Organ Class, Preferred Term and Reported term.

4.3.10 Protocol Deviations

A listing for individual participants will be presented to describe the participant level protocol deviations for this study based on the safety population.

4.3.11 Primary Objective Analysis

Change from Baseline will be calculated at each post-Baseline time point (4, 8, 12, 16, 20 & 24 weeks) for the primary DHEQ endpoints:

- Section 2
 - DHEQ Total Score (sum of Q1-34)

HLN-003 Statistical Analysis Plan		
Page 14 of 17	Version 1.0	

- DHEQ Restrictions Domain score (sum of Q1-4)
- DHEQ Adaptation Domain score (sum of Q5-16)
- DHEQ Social Impact Domain score (sum of Q17-21)
- DHEQ Emotional Impact Domain score (sum of Q22-29)
- DHEQ Identity Domain score (sum of Q30-34),

Change from Baseline in each DHEQ endpoint listed above will be analyzed using a MMRM with time point fitted as a fixed effect, the respective Baseline DHEQ score as a covariate and participant fitted as a repeated measure with unstructured covariance matrix. Kenward Rogers degrees of freedom will be applied. The estimates of the adjusted mean (standard error [SE]) change from Baseline will be presented along with 95% CIs.

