## 12 STATISTICAL CONSIDERATIONS AND DATA ANALYSES

## 12.1 Sample Size Determination

Sufficient participants will be screened (to allow for up to 50% screen failure rate) to ensure approximately 500 participants are enrolled and approximately 400 complete (to allow for up to 20% drop-out rate).

A sample size of 400 participants would ensure at least 90% power to achieve a statistically significant (two-sided 5% significance level) reduction in Baseline in DHEQ Total Score when using a one-sample t-test, assuming a true population effect size (mean reduction/standard deviation [SD]) of 0.2. The planned primary analyses (defined in Section 12.3.2) in this study will use a Mixed Model with Repeated Measures (MMRM) with time point as a fixed effect, Baseline DHEQ score as a covariate and participant as a repeated measure.

As well as providing adequate power to demonstrate statistically significant reductions from Baseline at each timepoint (4, 8, 12, 16, 20 & 24 weeks), 400 participants will ensure adequate precision of the corresponding 95% confidence intervals (CIs) for the mean reduction, and robust RWE relating to the magnitude of benefit from product use, at each timepoint. In a previous study (Haleon study 216953) assessing the same DHEQ-48 endpoints over 24 weeks in a RWE setting for an anti-sensitivity toothpaste containing 5% KNO3, the SD of the change from Baseline in DHEQ Total Score was shown to increase from around 30 units at Week 4 to 50 units at Week 24. An SD of 30 units and 50 units across 400 participants would equate to precision of the 95% CIs for the mean reduction within +/- 3 and 5 units, respectively.

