#### 12.3.1 Primary Analyses

Change from Baseline will be calculated at each post-Baseline time point (4, 8, 12, 16, 20 & 24 weeks) for the primary DHEQ endpoints:

#### Section 2

- DHEQ Total Score (sum of Q1-34)
- DHEQ Restrictions Domain score (sum of Q1-4)
- DHEQ Adaptation Domain score (sum of Q5-16)
- DHEQ Social Impact Domain score (sum of Q17-21)
- DHEQ Emotional Impact Domain score (sum of Q22-29)
- DHEO Identity Domain score (sum of Q30-34),

Change from Baseline in each DHEQ endpoint listed above will be analyzed using a MMRM with time point fitted as a fixed effect, the respective Baseline DHEQ score as a covariate and participant fitted as a repeated measure with unstructured covariance matrix. Kenward-Rogers degrees of freedom will be applied. The estimates of the adjusted mean (standard error [SE]) change from Baseline will be presented along with 95% CIs.

Clinical Protocol Template v10.0

Protocol Number: 300058

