4.1 Sample Size Calculation

Sufficient participants will be screened (to allow for up to 50% screen failure rate) to ensure approximately 500 participants are enrolled and approximately 400 complete (to allow for up to 20% drop-out rate).

A sample size of 400 participants would ensure at least 90% power to achieve a statistically significant (two-sided 5% significance level) reduction in Baseline in DHEQ Total Score when using a one-sample t-test, assuming a true population effect size (mean reduction/standard deviation [SD]) of 0.2. The planned primary analyses in this study will use a Mixed Model with Repeated Measures (MMRM) with time point as a fixed effect, Baseline DHEQ score as a covariate and participant as a repeated measure.

CC	HLN-003 Statistical Analysis Plan	
	Page 10 of 17	Version 1.0

As well as providing adequate power to demonstrate statistically significant reductions from Baseline at each timepoint (4, 8, 12, 16, 20 & 24 weeks), 400 participants will ensure adequate precision of the corresponding 95% confidence intervals (Cls) for the mean reduction, and robust RWE relating to the magnitude of benefit from product use, at each timepoint. In a previous study (Haleon study 216953) assessing the same DHEQ-48 endpoints over 24 weeks in a RWE setting for an anti-sensitivity toothpaste containing 5% KNO3, the SD of the change from Baseline in DHEQ Total Score was shown to increase from around 30 units at Week 4 to 50 units at Week 24. An SD of 30 units and 50 units across 400 participants would equate to precision of the 95% Cls for the mean reduction within +/- 3 and 5 units, respectively.

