4.3.12 Secondary Objectives Analysis

4.3.12.1 DHEQ, Secondary Endpoints

Change from Baseline will be calculated at each post-Baseline time point (4, 8, 12, 16, 20 & 24 weeks) for the secondary DHEQ endpoints:

- Section 1
 - Change from Baseline in Impact on Everyday Life: Q1, Q2, & Q3 (separate scores)
- Section 2
 - Change from Baseline in DHEQ Global Oral Health (Q35)
 - Change from Baseline in DHEQ Effect on Life Overall (sum of Q36-Q39)

Each DHEQ endpoint listed above will be analyzed using a MMRM with time point fitted as a fixed effect, the respective Baseline score as a covariate and participant fitted as a repeated measure with unstructured covariance matrix. Kenward-Rogers degrees of freedom will be applied. The estimates of the adjusted mean (SE) change from Baseline at each post-Baseline timepoint will be presented along with 95% Cls.

For each DHEQ endpoint listed above (Sections 4.3.13 and 4.3.14), and each individual DHEQ question, the score at each timepoint (including Baseline) and the corresponding change from Baseline (at each post-Baseline timepoint) will be summarized descriptively.

HLN-003 Statistical Analysis Plan	
Page 15 of 17	Version 1.0

Plots of mean score (SE) for each DHEQ endpoint listed above, and the individual DHEQ questions, over time will also be provided.

The number and percentage (%) of participants who 'agree' (score 5-7) with the 34 items (statements) in 5 domains of the DHEQ (Section 2, Q1-Q34) will be summarized at Baseline and Week 24. The percentage for each item will be summarized and presented in descending order of percentage at baseline.

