4.3.15 Missing Values

Missing data due to dropouts/withdrawals will be assessed on an ongoing basis during the study.

For the DHEQ data, for any timepoint if response is missing, it will be excluded from the primary analysis; the data available for each participant (even though some time points may be missing) will still be included in the analysis.

The MMRM approach will include all participants in the mITT population in the analysis. Any missing data from such participants will be treated as 'missing at random', i.e., their missing data at a particular time point will be assumed to behave in similar fashion to a participant with non-missing data at that time point who has similar data at other time points. This approach ensures an unbiased approach to handling missing data under the 'missing at random' assumption.

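### The single-arm change-score MMRM gives a CI too narrow for the mean reduction, and its single baseline slope can bias Week 24

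*SAP*

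**What the plan says.** The primary model in SAP 4.3.11 is an MMRM on change from Baseline with "time point fitted as a fixed effect, the respective Baseline DHEQ score as a covariate and participant fitted as a repeated measure", an unstructured covariance matrix and Kenward-Roger degrees of freedom. The output is stated as: "The estimates of the adjusted mean (standard error [SE]) change from Baseline will be presented along with 95% CIs". Protocol 12.3.1 gives the same model ("the respective Baseline DHEQ score as a covariate and participant fitted as a repeated measure with unstructured covariance matrix"). SAP 4.3.12.1 repeats it for the secondary DHEQ endpoints ("the respective Baseline score as a covariate and participant fitted as a repeated measure with unstructured covariance matrix"), and SAP 4.3.12.2 applies it to the NPRS.

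The study has one arm, so the adjusted mean is itself the result and there is no between-arm difference. Neither document includes a baseline-by-time term, names the baseline value at which the adjusted mean is taken, or allows in the variance for baseline being sampled.

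Precision is planned from the SD of change. In the sponsor's study of a 5% KNO3 toothpaste, "the SD of the change from Baseline in DHEQ Total Score was shown to increase from around 30 units at Week 4 to 50 units" (the second value is for Week 24). Protocol 12.1 says that these SDs with 400 participants "would equate to precision of the 95% CIs for the mean reduction within +/- 3 and 5 units, respectively". The stated purpose is "robust RWE relating to the magnitude of benefit from product use, at each timepoint". On missing data, SAP 4.3.15 says "This approach ensures an unbiased approach to handling missing data", and the sentence goes on to condition this on MAR.

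**The concern.** There are two separate faults.

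1. **The CI.** The sample-size text targets the population mean reduction and uses the unconditional SD of change. The model's SE treats the observed baselines as fixed. In a two-arm comparison the error in the baseline mean would largely cancel, but in a single arm it does not. If baseline correlates with change, the reported CI looks more precise than the plan intended and covers less than 95%. Kenward-Roger does not repair this, because it deals with estimation of the covariance parameters and not with sampling of the covariate.
2. **Bias.** One slope serves all visits. If the true slopes differ by visit and dropout depends on baseline, the common slope corrects the Week 24 mean by the wrong amount. MAR alone does not protect against this, because the mean model must also be right.

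The primary objective is descriptive. The size of change and its CI are the study's main product, so both faults fall on the headline result.

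**Working it through.** **Inputs from the documents:** n=400 completers, 500 enrolled, dropout up to 20%, two-sided 5%, effect size 0.2, SD of change 30 (Week 4) and 50 (Week 24).

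**Assumed, because the documents give none:** r, baseline SD (SD_B), residual correlation, and the dependence of dropout on baseline.

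**1. The plan's own figures reproduce.**
- Half-widths: 1.96 x 30/sqrt(400) = 2.94 and 1.96 x 50/sqrt(400) = 4.90.
- Enrolment: 400/(1 - 0.2) = 500.
- Power: noncentrality 0.2 x sqrt(400) = 4, which gives 97.9%.

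**2. What the model SE leaves out.** For the mean change at visit t,

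Var(mean change) = residual variance/n + slope_t^2 x Var(baseline)/n.

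The conditional SE keeps only the first term. With the correct slope at that visit, SE = SD x sqrt(1 - r^2)/sqrt(n) and coverage = 2 x Phi(1.96 x sqrt(1 - r^2)) - 1. At SD 50:
- r=-0.3: half-width 4.90 x 0.954 = 4.67, coverage 93.9%.
- r=-0.5: half-width 4.90 x 0.866 = 4.24, coverage 91.0%.

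The planned common-slope model leaves some baseline variance in the residual when slopes differ, so its loss is slightly smaller. Solving that model on complete data (SD_B 40 unless stated, five residual correlation structures) gives at Week 24:

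| Case | Coverage | Half-width (planned 4.90) |
|---|---|---|
| r=0 | 95.0% | 4.90 |
| r=-0.2 | 94.6% | 4.8 |
| r=-0.3 | 93.9-94.1% | 4.7 |
| r=-0.4 | 93.0-93.2% | 4.5-4.6 |
| r=-0.5 | 91.4-91.9% | 4.3-4.4 |
| Stable score spread, SD_B 50 | 92.0-92.9% | 4.4-4.5 |
| Stable score spread, SD_B 40 | 89.3-91.0% | 4.0-4.2 |

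A simulation without dropout (SD_B 35, r from -0.2 at Week 4 to -0.5 at Week 24) gave a model SE of 2.27 against an actual SD of 2.44 for the estimate, and coverage of 92.3%. Adding baseline-by-time alone lowered the SE to 2.17 and coverage to 91.5%. Adding the missing variance term as well gave 95.3%.

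**3. What the planned SDs imply about r and the slopes.** Var(score_t) = Var(B) + Var(change_t) + 2 Cov(B, change_t).
- Equal slopes at Weeks 4 and 24 need equal covariances, so the score variance must rise by exactly 50^2 - 30^2 = 1600 between those visits (for example SD 40 to 56.6), whatever SD_B is.
- r=0 at Week 24 needs score variance 2500 above baseline (SD 40 to 64).
- If the spread of scores is stable, r = -SD(change)/(2 x SD_B). That is -0.375 and -0.625 at SD_B 40, or -0.30 and -0.50 at SD_B 50, for Weeks 4 and 24.

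Total Score is 34 items scored 1 to 7, so its floor is 34. A large rise in spread during improvement towards a floor would be unusual. Negative r and unequal slopes are therefore plausible, but not proved.

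**4. Week 24 bias** (true change -10, 20% dropout, odds ratio (OR) of dropout per baseline SD):

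| Slopes or r, Week 4 to Week 24 | OR 1.5 | OR 2.0 |
|---|---|---|
| Equal slopes (SD_B 40) | 0.00 | -0.03 |
| Slopes -0.3 to -0.5 or -0.2 to -0.4 (SD_B 40) | about 0.3 | 0.7-0.8 |
| Slopes -0.28 to -0.78 (SD_B 40) | 1.0 | 1.8 |
| Slopes -0.15 to -0.75 (SD_B 40) | 1.2 | 2.1 |
| Four r patterns, shallowest -0.3 to -0.4, steepest -0.1 to -0.7 (SD_B 35) | 0.7-1.7 | 1.1-2.6 |

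Dropout unrelated to baseline gives essentially no bias, so both conditions are needed. If high-baseline participants leave, the bias is positive and understates the reduction. If low-baseline participants leave (OR 0.5), it is -1.0 to -2.5 and overstates it. In the two steep-slope rows at SD_B 40, coverage was 87% at OR 1.5 and 80-81% at OR 2.0.

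**5. The unstated reference baseline matters.** The figures above use the participant-mean baseline. If software averages baseline over records instead, early leavers count less, and bias is 0.7-1.1 units even with equal slopes and 1.7-3.0 with unequal slopes.

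**The case against.** The strongest reply is that a conditional SE is conventional and the CI is valid for change at a fixed reference baseline. That is true, but the SAP declares no such target and no reference value, and its sample-size section speaks of the mean reduction with the full SD. The mismatch stands.

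Other points carry some weight:

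- **Raw summaries.** The plan includes mean, SD and SE of raw change at every visit, so the wider SE will be visible. Those summaries do not use the MMRM's MAR handling, however, and in the steep-slope and equal-slope dropout scenarios at SD_B 40 they were off by 1.4 to 4.4 units.
- **Size.** At r=-0.3 the shortfall is about one point of coverage and 0.2 units. With milder slopes the bias is 0.3 to 0.8 units, and about 0.2 at OR 1.2. This is fair, and the larger figures should not be read as expected values.
- **Borrowed SDs.** The 30 and 50 come from another toothpaste, and the identity in step 3 needs the same participants at both visits. This limits what can be said about this trial, but not the mechanism.
- **MAR and sensitivity analyses.** The unbiasedness sentence is qualified by MAR, and Protocol 12.3.6 leaves room for further sensitivity analyses at data review. Neither addresses the mean model or the CI, and no specific analysis is named.
- **Consistency.** The model is also fixed in the Protocol, so a change confined to the SAP would create a conflict. This is correct and affects the fix.

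**Conclusion.** The concern holds and should be fixed before the analysis. The reported CI does not match the plan's stated target unless r=0. Week 24 coverage falls to about 94% at r=-0.3, 91.4-91.9% at r=-0.5, and 89-91% if score spread is stable at an assumed baseline SD of 40. The bias is conditional: it needs slopes that differ by visit together with dropout that depends on baseline, and its direction depends on who leaves. At 20% dropout and odds ratios of 1.5 to 2.0 its size was about 0.3 to 2.6 units, against a planned precision of +/-5.

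Confidence in the mechanism is high. How far it bites here is unknown, since the documents give no baseline SD, correlation or dropout pattern. The overall conclusion is unlikely to change: success is defined only as a trend of improvement, and at the planned effect the test statistic is about 4. What is affected is the reported Week 24 size and its error bars.

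**What to change.** In SAP 4.3.11, 4.3.12.1 and 4.3.12.2, fit the MMRM to the scores themselves with Baseline as the first repeated response. Use time as a factor (7 levels for DHEQ, 9 for NPRS), unstructured covariance and Kenward-Roger, and report each visit-minus-Baseline contrast with its SE and 95% CI. In the simulations at SD_B 40 this gave bias within 0.1 units and coverage of 94.6-95.4% under baseline-dependent dropout.

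The alternative is to keep the change-score model with three additions:
- a baseline-by-time term;
- a statement that adjusted means are taken at the mean baseline of all mITT participants, not the mean over records;
- slope_t^2 x Var(baseline)/n added to each variance, with the degrees of freedom for the enlarged variance defined.

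The interaction alone makes the CI narrower and is not a fix.

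In SAP 4.3.15, state that unbiasedness requires MAR and a correctly specified mean model. Mirror the model in Protocol 12.3.1 and 12.3.2, with the matching text in the synopsis and 12.1, or document the change from protocol.

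The cost is wording and a small program change, with no new data. CIs return to the planned width (2.94 and 4.90 at n=400), and the power claim is unaffected (97.9% against the stated 90%).

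### Every MMRM uses one Baseline slope for all visits; if the slope changes and dropout depends on Baseline, later visit means are modestly biased, and a Baseline-by-visit term evaluated at the mITT mean Baseline removes this

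*SAP*

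**What the plan says.** SAP 4.3.11 analyses change from Baseline in the Total Score and the five domain scores at six visits. Time point is a fixed effect, with "the respective Baseline DHEQ score as a covariate and participant fitted as a repeated measure with unstructured covariance matrix". Protocol 12.3.1 gives the same model. SAP 4.3.12.1 repeats it for the secondary DHEQ endpoints, with "the respective Baseline score as a covariate and participant fitted as a repeated measure with unstructured covariance matrix", and SAP 4.3.12.2 applies identical methods to NPRS at eight visits. No section adds a Baseline-by-time point term.

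On output, SAP 4.3.11 says: "The estimates of the adjusted mean (standard error [SE]) change from Baseline will be presented along with 95% CIs". It does not give the Baseline value at which the adjusted means are evaluated.

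SAP 4.3.15 treats missing data as missing at random and describes the resulting approach as unbiased under that assumption. SAP 4.1 allows for up to 20% dropout. SAP 4.3.2 requires residual analyses but names no check of the Baseline slope.

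**The concern.** With Baseline as a main effect only, the regression of change on Baseline is forced to be the same at Week 4 and Week 24. With complete data this does not distort the visit means at the mean Baseline. With dropout, the model uses the slope to carry the mean from those still observed to those who left. If the slope is wrong for that visit and the leavers differ at Baseline, the adjusted mean is wrong too.

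Dropout that depends only on Baseline is missing at random. The plan's claim of unbiasedness therefore also needs a correct mean model, and this is the part left unprotected. The study is single-arm, so there is no comparator in which such an error could cancel, and SAP 4.1 presents the size of benefit at each visit as a product of the study.

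There is a reason to expect a changing slope. The Total Score sums 34 items scored 1 to 7, so its floor is 34. A participant starting at 68 can improve by at most 34 units, while one starting at 204 can improve by up to 170. That limit matters more as improvement accumulates.

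**Working it through.** **Plan's own figures (SAP 4.1).**
- Power: N = 400 and effect size 0.2 give noncentrality 0.2 × √400 = 4. Two-sided 5% power of the one-sample t-test is 97.9%, so the stated minimum of 90% is met.
- CI half-widths: 1.96 × 30/√400 = 2.94 and 1.96 × 50/√400 = 4.90, matching the stated 3 and 5.
- Enrolment: 400/(1 − 0.20) = 500.
- Scale for what follows: planned Week 24 effect 0.2 × 50 = 10 units; SE 50/√400 = 2.5.

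**Mechanism.** Let β_t be the true slope at visit t, b the fitted common slope, B̄ the mITT mean Baseline and B̄_t the mean Baseline of those observed at t. To a first approximation

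bias_t ≈ (b − β_t) × (B̄ − B̄_t).

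It vanishes if b = β_t or if B̄_t = B̄, so both conditions are needed.

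**Simulation.** From the documents: six visits, SD of change rising from 30 to 50, about 20% dropout by Week 24, unstructured covariance. Assumed, because the documents do not give them: Baseline SD, slopes by visit, and the dropout odds ratio (OR) per Baseline SD, with higher-Baseline participants leaving more. The residual correlation is also assumed: autoregressive (AR) 0.85 or exchangeable 0.6. Each scenario has 60,000 participants. Cells give Week 24 bias in Total Score units for the common-slope model / the interaction model, both evaluated at the mITT mean Baseline, with Baseline SD 40.

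| Slope, Week 4 to Week 24 | OR | AR 0.85 | Exchangeable 0.6 |
|---|---|---|---|
| −0.3 to −0.5 | 1.5 | 0.45 / 0.00 | 0.54 / −0.01 |
| −0.3 to −0.5 | 2 | 0.80 / 0.08 | 0.92 / 0.07 |
| −0.2 to −0.6 | 2 | 1.40 / 0.00 | 1.70 / −0.04 |
| −0.2 to −0.6 | 3 | 2.17 / 0.06 | 2.47 / −0.13 |
| −0.1 to −0.8 | 3 | 3.34 / 0.01 | 4.20 / −0.04 |
| −0.4 constant | 2 | 0.02 / 0.01 | 0.05 / 0.09 |

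- In the third row (AR) the fitted common slope is −0.26 and those observed at Week 24 average 5.81 units lower at Baseline. The formula gives (−0.26 + 0.60) × 5.81 = 1.98; the simulation gives 1.40. The unstructured covariance recovers part of the error but not all of it.
- Across all changing-slope scenarios, including Baseline SD 30, the common-slope bias is 0.3 to 4.2 units at Week 24 and 0.1 to 0.8 at Week 12. The interaction model stays within about 0.2 of zero.
- A milder case (slope −0.15 to −0.50, log-odds ±0.6 per Baseline SD) gives about ±1.1, against 0.1 or less with the interaction.
- With a changing slope but dropout unrelated to Baseline, the bias is 0.10 (Monte Carlo SE 0.12).
- Sign: positive means improvement is understated. It reverses if low-Baseline participants leave more.

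**Effect on the interval.** A bias of 1 to 1.5 units is 1/2.5 = 0.4 to 1.5/2.5 = 0.6 SE. Normal coverage becomes Φ(1.56) − Φ(−2.36) = 93% to Φ(1.36) − Φ(−2.56) = 91%, instead of 95%.

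**Evaluation point.** A Baseline mean taken over analysis records counts each participant once per completed visit and so under-represents leavers. Evaluated there, the interaction model still misses the mITT mean by 0.6 to 3.3 units at Week 24 (common slope 0.7 to 5.1).

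**Cost.** Across 300 simulated trials of N = 500 with a truly constant slope, the Week 24 SE ratio (interaction/common) was 1.002 with Baseline-dependent dropout and 0.999 without.

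**The case against.** A reader might infer from SAP 4.1, where the SD of change "was shown to increase from around 30 units at Week 4 to 50 units at Week 24", that a constant slope is implausible. The documents do not support that. With Baseline SD 40 and a constant slope of −0.4, Baseline explains 0.16 × 1600 = 256 of the variance at every visit. Residual SDs of √(900 − 256) = 25.4 and √(2500 − 256) = 47.4 then reproduce 30 and 50. Even slopes of −0.15 to −0.50 account for only (0.25 − 0.0225) × 1600 = 364 of the 2500 − 900 = 1600 rise in variance. The figures also come from an earlier study of a different toothpaste. What can be said is narrower: a constant slope requires the variance of the follow-up score itself to grow by exactly 1600, and the documents do not say whether it does.

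A reader might also treat Week 24 as the headline estimate. The plan gives all six visits and six primary endpoints equal standing, and the bias is largest at the last visit. The primary objective is descriptive, and success is an observed trend towards improvement, which a bias of this size would be unlikely to overturn.

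The 20% dropout is of enrolled participants. Some of them will have no post-Baseline DHEQ and fall outside mITT, so missingness within mITT may be lower unless skipped visits add to it.

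These points stand. They limit how likely and how large the bias is, but they do not remove it where the two conditions hold.

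**Conclusion.** The point holds in conditional form. The plan fits one common Baseline slope, and if the slope varies by visit and dropout depends on Baseline, later adjusted means are biased under the plan's own missing-at-random assumption. Under the assumed inputs the Week 24 bias in Total Score is roughly 0.3 to 4 units, typically 1 to 1.5, in a direction that cannot be known in advance. At the mITT mean Baseline it was below the 4.9-unit half-width in every scenario. It is about zero if either condition fails.

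The documents do not support saying that this trial's estimates will be biased: they give no Baseline SD, no slope by visit and no link between Baseline and dropout. Nor do they support saying that the interaction alone is a complete and free repair. The evaluation point has to be named as well, and the cost is negligible rather than nil. Sample size is unaffected. This is a cheap improvement, worth making before the analysis is run.

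**What to change.** In SAP 4.3.11, 4.3.12.1 and 4.3.12.2, and in protocol 12.3.1 and 12.3.2 (with the synopsis summary), add the Baseline score-by-time point interaction to every MMRM. State that adjusted means at each visit are evaluated at the mean Baseline score of mITT participants, one value per participant, and not at the mean over analysis records.

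The cost is 6 − 1 = 5 extra parameters per DHEQ model and 8 − 1 = 7 for NPRS, with an SE ratio of about 1.00 and no new data. If the slope is in fact constant, the extra term does no harm.

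The change does not address dropout that is missing not at random, or participants with no post-Baseline DHEQ, whom the mITT definition in SAP 4.3.3 excludes. Those need separate handling.
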